VO₂max - Maximal Oxygen Uptake
VTE - Venous Thromboembolism
400MWT - 400-Meter Walk Test

Introduction

This document is a protocol for a human research study. This study is to be conducted in accordance with applicable Federal regulations and institutional research policies and procedures.

Older adults with type 2 diabetes (T2D) experience an accelerated rate of sarcopenia, which is the deterioration in muscle mass, strength, and physical performance. Periods of disuse caused by illness or hospitalization causes rapid loss of muscle mass and strength, which negatively impact physical function upon re-ambulation. In fact, without adequate rehabilitation, physical function does not fully recover in older adults following disuse, reducing the quality of life and loss of independence.

There is a lack of effective therapeutic options to aid muscle recovery following disuse, in part, because the myocellular mechanisms underlying the atrophy and recovery programs in human muscle are not well characterized. Our long-term goal is to identify specific molecular targets for the development of evidence-based clinical interventions to counteract the negative health outcomes associated with muscle atrophy induced by illness, injury, or hospitalization. Our overall objectives are to employ highly innovative methods in muscle biopsy specimens in order to decipher the temporal sequence by which mitochondrial dysfunction and lipotoxicity in older adults with T2D impact atrophy and recovery of muscle mass, strength and physical function following bed rest. Studies in the clinically relevant context of aging, T2D and exercise will provide a physiological framework in which the temporal and mechanistic relationships between mitochondria, intramyocellular lipid and protein synthesis/breakdown can be interrogated during atrophy and recovery.

Our primary approach is to conduct a prospective, parallel two arm, randomized controlled study consisting of five discrete but connected phases:

I) Screening, II) Pre-Bed Rest, III) Bed Rest, IV) Ambulatory/Exercise Recovery and V) Resistance Exercise (OPTIONAL)

Eligible participants will be Older Adults with T2D and will be randomly assigned to one of two groups: Exercise recovery (EX) or Ambulatory recovery (CON).

The expected duration for a subject in this study could be up to 16 weeks.

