A series of physiologic and clinical/health outcomes will be assessed before, during and after the bed rest intervention period and recovery period:

1) Morning resting fasted variables: blood pressure; blood glucose and lipids. 2) Physical Examination, Resting EKG, Urine collection (for urinalysis, BUN, creatinine). 3) Cardiorespiratory fitness (VO₂peak) determined via a graded cycle ergometry test. 4) Body composition by; DXA scan - bone mineral density, total and partitioned lean mass, estimated visceral fat; and MRI – left and right leg mid-thigh muscle, bone and fat volume and area. 5) Muscle strength and power: Quadriceps muscle performance testing (maximal strength and power)

will be performed using a Biodex dynamometer. 6)Physical function: The Short physical performance battery (SPPB) will be used to measure lower extremity performance as a secondary outcome. 7) MRS: Mitochondrial energetic capacity (ATP_{max}) will be determined by ³¹P MRS with a brief (24 sec) bout of isometric exercise protocol. 8) Hyperinsulinemic euglycemic clamp to determine insulin sensitivity.

Participants will enter a 10-day strictly controlled bed rest intervention at the Translational Research Institute (TRI) clinical research unit and a progressive 4-week aerobic and resistance training recovery program at the exercise training facility at the TRI, if not randomized to the ambulatory recovery group. Both groups can also receive additional optional resistance exercise training following 4 weeks of the ambulatory or exercise recovery phase. Blood and skeletal muscle biopsies will be collected immediately following days 10 of the bed rest period and after 1, 2, 3 and 4 weeks of the recovery period. Adipose tissue biopsies will also be collected on bed rest day one, immediately following 10 days of bed rest, and after 4 weeks of recovery if the participant elects to do this. The adipose biopsy is available to be chosen by the participant but not required.

Background Information and Scientific Rationale

Premise: **Skeletal muscle atrophy is a clinically significant problem that occurs during disuse or immobilization** due to hospitalization, illness and injury, and leads to a loss of muscle strength and physical function (28, 42, 66). This is a particular public health problem for older adults who comprise the majority of hospital patients in the US (26, 38) and who may lose more muscle mass during bed rest (64, 88).

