Older adults do not adequately recover following bed rest without adequate rehabilitation (57, 112, 113), which likely contributes to their reduced functional status and ambulation upon discharge (20, 22), a loss of independence, nursing home placement (39) and an increased risk for falls and fractures (80). Older adults are also more likely to develop type 2 diabetes (T2D). Indeed, ~33% of all hospital patients in the US have T2D. Evidence from the longitudinal Health ABC study showed that T2D is associated with more rapid loss of muscle mass and strength in older adults (89). Furthermore, older adults with T2D are at increased risk of injurious falls (78) and physical disability (25). Despite the potentially serious clinical implications however, T2D has not been investigated as an important factor in muscle atrophy and recovery response with immobilization.

Mechanisms underlying disuse atrophy and poor muscle recovery in humans are not well characterized. Most immobilization studies in humans have been limited to measuring changes in muscle only before and after disuse atrophy and recovery (20, 21, 64, 65, 113, 114). This has contributed to discordant views in the field regarding the causal roles that deranged protein synthesis or degradation play in atrophy responses (43, 94, 96). Supported by evidence from preclinical rodent models (8), clinical investigations of early time course changes during atrophy and recovery responses could reveal temporal mechanistic relationships, leading to identification of muscle targets in humans. For example, only 24-48 hrs. of inactivity can reduce muscle protein synthesis (115), and reduce phosphorylation of AKT, a key upstream regulator of mTOR/p70S6K (111, 118).

The role of mitochondrial energetics in disuse atrophy in humans is unknown. The metabolic correlates to muscle atrophy include skeletal muscle insulin resistance (21, 23, 75), decreased fatty acid oxidation and a shift to glucose oxidation (9), intramyocellular lipid accumulation (23, 110) and impaired protein synthesis (36, 42, 87). While mitochondria have been implicated in the etiology of these metabolic dysfunctions in the context of aging and diabetes (44, 92), the role of mitochondria in human muscle disuse atrophy and loss of function is poorly understood.

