Effective therapeutic strategies to prevent muscle atrophy and aid in recovery are lacking. Pharmacological therapies to date have focused on increasing muscle mass and include testosterone, selective androgen receptor modulators (SARMS), growth hormone, and myostatin antibodies that are currently at early phase clinical trials (81). Dietary supplements enriched with leucine and essential amino acids can promote protein synthesis (119). There is a critical need, however, to test mechanism-based approaches to prevent or attenuate atrophy and aid recovery following periods of inactivity for older adults.

Exercise as a strategy to aid recovery. Exercise interventions can clearly improve mitochondrial energetics, alleviate IR and stimulate protein synthesis resulting in improved muscle mass and strength (10). However, older adults with T2D are reported to have an attenuated improvement in health outcomes following exercise (109). *In context of recovery from bed rest, the efficacy of exercise to facilitate recovery of muscle mass, strength and function in older adults with T2D has not been determined.* We have shown that aerobic exercise improves insulin sensitivity, mitochondrial function and lowers sphingolipid in muscle from older adults and in obesity (33), and others have demonstrated reductions in oxidative stress (102). Here we propose to test the efficacy of exercise to facilitate recovery following bed rest, and to use exercise as a physiological tool to examine the relationships between improved mitochondrial energetics, lipid partitioning,

protein synthesis and IR during recovery. This could also emphasize mitochondria as an adjunct target to anabolic therapies.

Study Objectives

The overall objective of this project is to decipher the temporal sequence by which exercise training alters mitochondrial dysfunction and muscle protein synthesis in older adults with T2D and how an exercise intervention can aid in recovery of muscle mass, strength and physical function following bed rest. Studies in the clinically relevant context of aging, T2D, and exercise will provide a physiological framework in which the temporal and mechanistic relationships between mitochondria, intramyocellular lipid and protein synthesis/breakdown can be interrogated during atrophy and recovery.

Study Design

Research Design

The proposed clinical study is a prospective, parallel two arm, randomized controlled study consisting of five discrete but connected phases:

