Our group has performed more than 1,500 muscle biopsies during the past 20 years (600 during the past 4 years since the move to the TRI), including same day serial biopsy studies and studies in men and women over 90 years old (14, 17-19, 34, 35). We will conduct 1 biopsy immediately post bed rest (day 10) and 4 biopsies of the vastus lateralis during the ambulatory or exercise recovery interventions. The approximate locations of the biopsies will be balanced as indicated to avoid interference from previous muscle biopsies (See Figure). A biopsy of the Vastus Lateralis muscle will be performed using the Bergstrom technique. Subjects will be placed in a supine position and the skin will be cleansed with chlorhexidine solution. After a sterile drape is placed over the skin, local anesthesia will be administered using lidocaine. The skin will be incised (approximately 0.5 cm) with a #11 scalpel, and the Bergstrom needle will be inserted into the Vastus Lateralis. Approximately 150 mg of muscle tissue will be obtained under suction. After the biopsy, pressure will be applied to stop bleeding and the skin will be closed with steri-strips (suture(s) if allergy to steri-strips). A sterile dressing will be applied. An MD, DO, NP, or PA will conduct this procedure. This procedure is well-tolerated in older adults. Subjects will not perform physical exercise 48 hours prior to the muscle biopsy to help prevent acute effects of exercise on muscle lipid and the other primary outcomes. Muscle specimens will be trimmed of any visible adipose and connective tissue using a dissecting microscope and processed. The following assays will be performed on the muscle biopsy specimens:

1. Mitochondrial respiration will be measured in permeabilized muscle fibers from vastus lateralis biopsies using the Oxygraph 2K system (Oroboros, Innsbruck, Austria). This approach permits a comprehensive evaluation of mitochondrial respiratory function upon titration with ETC complex-specific

inhibitors and substrates (56). We assess complex I+II supported respiration and palmitate β -oxidation supported respiration in separate assay protocols. Submaximal and maximal, coupled and uncoupled respiration will be evaluated along with coupling control ratios. This technique is well established in our laboratory (16, 19, 35) and we have conducted respirometry assays in over 500 muscle biopsy specimens in recent years.

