from out bed rest and recovery study in older adults (recovery in leg lean mass over 4 weeks (n=20; mean \pm SD) = $+1.2 \pm 0.5$ kg). Sex will be explored as a biological variable, however, based on data from our previous bed rest and recovery study we do not expect a difference in rate of recovery between men and women (n=10 men $+1.1$ kg, n=10 women $+1.0$ kg lean mass recovery). The sample size will also provide 80% power to detect a significant mean difference of 0.38 AU in muscle mitochondrial OXPHOS protein expression between groups during recovery. The power calculations are based on two-sample t-tests for mean difference with unequal variance and a P-value of 0.05.

Statistical Analysis Plan

The **primary** outcomes, including leg lean mass, protein synthesis rate, and mitochondrial respiration, will be measured at 5 time points following 10 days of bed rest. 2x5 repeated-measures ANOVA will be performed on the dependent variables as a function of intervention (2 levels: EX and CON groups) and time (3 levels: 5x biopsy timepoints). We will also fit mixed models (fixed and random effects) to interrogate the longitudinal data. This will allow us to better account for the longitudinal nature of the data and to explore the influence of other potential predictors of changes in muscle mass. In particular, the relationship between change in IR, protein synthesis and mitochondrial function will be explored. Since many of these outcome variables are from biopsies, e.g., various mitochondria parameters will be correlated with one another, covariance will be explored, and we will also use the relative change measures of these as a bivariate outcome. Sex, race and ethnicity as biological variables will also be explored. Sex will be explored as a biological variable, however, based on data from our previous bed rest and recovery study we do not expect a difference in rate of recovery between men and women (n=10 men $+1.1$ kg, n=10 women $+1.0$ kg leg lean mass recovery).

Potential Risks and Benefits

Potential Benefits

Participants will likely receive no direct benefit from taking part in this research study.

Potential Risks

Blood draws and/or IV (lab samples, e.g.). There is a risk of pain, vasovagal syncope, hematomas, and/or infection at the blood draw site or IV insertion site (low risk of serious AEs).

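### The objectives extend to atrophy, but biopsy, tracer and clamp outcomes have no pre-bed-rest value, and the stated analysis does not use the one pre-bed-rest value that a primary outcome has

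*Protocol*

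**What the plan says.** The protocol's Introduction sets out to use muscle biopsy specimens to establish, as an order of events in time, how "mitochondrial dysfunction and lipotoxicity in older adults with T2D impact atrophy and recovery of muscle mass, strength and physical function following bed rest". The second sentence under Study Objectives says that the relationships between mitochondria, intramyocellular lipid and protein synthesis and breakdown "can be interrogated during atrophy and recovery".

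On sampling, the Introduction says that "skeletal muscle biopsies will be collected immediately following days 10 of the bed rest period and after 1, 2, 3 and 4 weeks" of recovery. Its list of outcomes, under a header that covers the time before, during and after bed rest and recovery, includes "Hyperinsulinemic euglycemic clamp to determine insulin sensitivity".

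On analysis, the Statistical Analysis Plan section says that the primary outcomes (leg lean mass, protein synthesis rate and mitochondrial respiration) "will be measured at 5 time points following 10 days of bed rest". It plans a 2x5 repeated-measures ANOVA (group by time), followed by mixed models that explore other predictors, which it does not list. Study Outcome Measures (Endpoints) gives the same five occasions: immediately after bed rest and weeks 1 to 4. The Phase II section calls pre-bed-rest day 1 the study baseline.

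**The concern.** A single value at the end of bed rest, with nothing before it, cannot show what bed rest changed. The background section criticises earlier work on the ground that "Most immobilization studies in humans have been limited to measuring changes in muscle only before and after disuse atrophy and recovery". For tissue, tracer and clamp measures this design lacks even the before value. Claims that altered respiration, ceramide or protein turnover accompanied the loss of muscle would have no within-person change behind them.

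The second issue concerns the word recovery. The Introduction describes the clinical problem as failure to regain full function after disuse. An analysis that starts at the end of bed rest measures gain from the low point. It does not say whether the loss was made good, although the scan needed for that is already scheduled.

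**Working it through.** No stated figure is in dispute, so the check is a count of measurement occasions followed by a short identity.

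**Inputs.** The pre-bed-rest table (Phase II); the bed-rest table and its footnotes on biopsy, clamp and D2O (Phase III); the recovery table (Phase IV); and the DXA paragraph under Potential Risks. The biopsy footnote reads "We will conduct 1 biopsy immediately post bed rest (day 10) and 4 biopsies of the vastus lateralis" during recovery. The clamp footnote places the first clamp on day 10 and says that bed rest ends when it is complete. The D2O footnote starts dosing in the first week after bed rest, while the bed-rest table marks days 10 and 11.

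| Measure | Before bed rest | End of bed rest | Recovery | Total |
|---|---|---|---|---|
| Muscle biopsy | 0 | 1 | 4 | 5 |
| Clamp | 0 | 1 | 1 | 2 |
| DXA | 1 | 1 | 4 | 6 |
| MR (ATPmax, IMCL, IMAT) | 1 | 1 | 4 | 6 |

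**Agreement with the plan's own figures.** Muscle biopsies: 0 + 1 + 4 = 5, matching the five stated time points. DXA: 1 + 1 + 4 = 6, matching the six scans counted under Potential Risks. D2O has no occasion before about day 10.

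**Change across bed rest.** Write P for the pre-bed-rest value, E for the end-of-bed-rest value and W for week 4. The bed-rest loss is P − E.
- For respiration, H2O2 emission, lipidomics, protein turnover and clamp insulin sensitivity, P does not exist, so P − E cannot be estimated by any analysis.
- For leg lean mass, P exists, but the five analysed occasions run from E to W. Six are collected and five analysed, and the unused one is the only pre-bed-rest value of any primary outcome.

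**Completeness of recovery.** W − P = (W − E) − (P − E). Sample Size Determination quotes a mean recovery of 1.2 kg in leg lean mass over 4 weeks from the group's previous study. With loss L = P − E, W − P = 1.2 − L. The same 1.2 kg is incomplete recovery if L exceeds 1.2 kg and more than complete if L is smaller. The stated analysis estimates W − E only.

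**Precision for the unused contrast (illustration).** For a paired change, the detectable mean at two-sided 0.05 and 80% power with n = 30 is 0.529 × SD of the change. The n assumes 15 completers per group, 2 × 15 = 30; the protocol gives 15 without saying per group, and 20 started per group × 0.75 = 15. The SD of the bed-rest change is not in the protocol. Assumed values of 0.3, 0.5 and 0.7 kg give 0.16, 0.26 and 0.37 kg.

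**The case against.** The strongest reply is that this is a recovery trial. The first sentence under Study Objectives concerns exercise training and recovery, and the primary outcomes, sample size and randomisation all follow it. The groups diverge only after bed rest, so its end is a legitimate starting point for the comparison. This stands, and it limits the point to the wider wording on atrophy and to the unused baseline.

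Several stronger readings are tempting, and the documents do not support them:
- A reader might infer that the trial can say nothing about atrophy. Leg lean mass, ATPmax, IMCL, IMAT and strength are measured before and after bed rest, which allows a two-point description. The day-10 tissue and clamp values also describe the end-of-disuse state and can be related to measured loss of lean mass.
- A reader might infer that no clamp or tracer dose falls within bed rest. The clamp footnote puts the first clamp inside it, and the table marks D2O on day 10. What is missing is a value from before.
- A reader might take the Introduction's outcome list as promising a pre-bed-rest clamp. Its header covers a mixed list collectively, so this calls for clarification and is not a firm contradiction.
- A reader might infer that the baseline data are discarded. The mixed models do not exclude them, and a separate analysis plan may cover the non-primary measures. The accurate statement is that the stated primary analysis does not use pre-bed-rest leg lean mass.

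The optional adipose biopsy on bed-rest day 1 does not fill the gap, because it is not muscle.

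**Conclusion.** The point holds in this limited form. The objectives reach further than the schedule: 0 of 5 muscle biopsies and 0 of 2 clamps precede the end of bed rest, and D2O starts at about days 10 to 11. Two of the three primary outcomes, protein synthesis and respiration, therefore have no pre-bed-rest value, and no later analysis plan can supply one. The third, leg lean mass, has one, and the stated 2x5 analysis leaves it out, so that analysis estimates neither the bed-rest loss nor the completeness of recovery.

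A reader might go on to infer that the comparison of the two recovery groups is compromised. It is not: that contrast lies wholly after bed rest. What changes is what may be claimed about atrophy and about full recovery. The conclusion rests on the schedules as printed, read with their footnotes where the tables are hard to follow.

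**What to change.** 1. In the Introduction and Study Objectives, limit the biopsy, tracer and clamp objectives to the recovery phase. In the Introduction's outcome list, state that the clamp has no pre-bed-rest assessment.
2. Add the paired change from before bed rest to the end of bed rest in leg lean mass, with a confidence interval. Report the same change descriptively for ATPmax, IMCL, IMAT and strength.
3. Enter pre-bed-rest leg lean mass as a covariate in the planned mixed model. It is measured before the recovery programme starts, so the programme cannot affect it. Report, by group, the week-4 difference from the pre-bed-rest level in kg with a confidence interval.
4. Do not express recovery as a ratio to the bed-rest loss. (W − E)/(P − E) has E in both numerator and denominator, and the denominator is small: Potential Risks expects a mass loss of about 3%. The ratio would be unstable and mathematically coupled.

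The cost is a change of wording, a little more analysis and a narrower mechanistic claim about atrophy. All the data are already in the schedule, so no visit or procedure is added.
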